5.3 Handling of Dropouts or Missing Data

Unless otherwise specified, missing data will not be imputed. Subjects who drop out will not be replaced and all available data will be used.

5.3.1 Diary Data

Daily diary entries by the subject are made directly onto paper CRFs and are, therefore, "self-sourcing" source data. If a subject does not bring the original (O) diary to the clinic visit, then the site will ask the subject to recall the data on a diary copy (C). The copy will be used until the original is returned at a following clinic visit. During the first 24 months of the study, the diary data for bleeding, cramping and other contraception use will be recorded by the subject on a daily basis. Beginning after month 24, the subject will continue to record other contraception use on a daily diary but bleeding and cramping information will be characterized on a bleeding/cramping form completed by the site through subject interview approximately every 3 months.

If the original diary becomes available after the data from the copy have been entered into the study data base, the data base will be updated to include the original diary data along with the copy. The data base audit trail will reflect initial data entry from the copy followed by subsequent entry of the original. Diaries returned by the subject that include days when no information was obtained have those data records included in the data base. However, no such blank records are in the data base for entire diary pages that may have not been returned, e.g., the subject may have returned diaries for March and May but never returned the April diary. In these cases, missing data are not part of the data base but are accounted for as blank records in the same manner as those which appear, essentially at random, within a returned diary. Since the diary day counting process for identification of 28-day cycles when another birth control method use was reported looks at each diary date record relative to the IUS insertion date, the presence of missing diary records will not affect this calculation. The extent and magnitude of missing diary records will be assessed and presented as part of overall diary results.

Diary numbers on CRFs will not be used; only the date information on the CRF will be used. If the date recorded does not exist, the data will not be included. If the subject never returns the original copy, the copy will be used for analyses. Duplicate diary records (e.g., an original and a clinic copy) for the same study day can appear in the study data base and should be handled as follows:

- If the diaries represent an original diary and a clinic copy diary, the original diary data will serve as the diary data of record.
- If the diaries are submitted as duplicates of the same original or same clinic copy, the most recently submitted version will be used for analyses.

Bleeding and cramping categories are listed below in order of increasing severity.

- Bleeding: None, Spotting, Light Flow, Normal Flow, Heavy Flow.

- Cramping: None, Mild, Moderate, Severe.

Note: In an early version of the diary, this information was recorded as None, Spotting, or Bleeding. In the analysis, if the subject did not complete a revised diary, the category of “bleeding” will be considered “Normal Flow.”

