5.3.2 Bleeding, Cramping, and Other Contraceptive Use

For the categories of bleeding, cramping and other contraception use, no imputation of data from the diaries will be done for missing data. For example, a subject with completely missing data for a particular diary day will be considered as having no reported bleeding, no cramping, no other contraceptive use, etc. for that day. Missing data for, say, bleeding alone will be considered as the subject having no reported bleeding for that day.

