9.2 Primary Efficacy Variable

The primary efficacy variable is the Pearl Index, an estimation of the number of unintended pregnancies per 100 women-years of exposure. The Pearl Index is calculated as the number of "on treatment" pregnancies in the study divided by the total number of complete 28-day cycles of use (as defined in Section 5.5) in the study across all participating subjects, that result multiplied by 1300 (13 cycles x 100 years). In the case of subjects who are still on study at the time of a Pearl Index calculation, the last known date of product use (defined in Section 5.4) will be used in place of the IUS discontinuation date. A "last cycle" computed using this algorithm will be considered complete if it is at least 23 days in length. In addition, subjects who become pregnant will have that last cycle counted as completed for the Pearl Index calculation, regardless of length.

For the primary Pearl Index outcome using exposure information through Year 5, the MITT population will be used as the basis of exposure and all 28-day cycles where use of another birth control method was reported in the daily diary will be excluded from the total cycle count denominator. Diary days when no information regarding the use other birth control methods is reported will be considered days when no other birth control method use took place. The Pearl Index will be calculated using both the cumulative data

through Year 10 and as individual, non-cumulative year-by-year estimates (see Section 10.1).

For the definitive assessment of contraceptive efficacy, the Pearl Index and its 95% confidence interval will be considered the primary result for inferences.

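### A diary day left blank on the original displaces a positive entry on the clinic recall copy and is analysed as none

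*SAP*

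**What the plan says.** SAP 5.3.1 (Diary Data) provides for a recall copy when the original is not brought to the visit. On its status the section says "The copy will be used until the original is returned at a following clinic visit", and also "If the subject never returns the original copy, the copy will be used for analyses". When the original arrives after the copy has been entered, both are held in the database with an audit trail.

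The section accepts that duplicate records "for the same study day can appear in the study data base and should be handled as follows", and the rule for this pair is "If the diaries represent an original diary and a clinic copy diary, the original diary data will serve as the diary data of record".

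The same section covers blank days: "Diaries returned by the subject that include days when no information was obtained have those data records included in the data base". So a blank day on a returned original is a record in its own right.

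Two other sections give a blank its meaning. Under SAP 5.3.2, a subject with nothing recorded for "a particular diary day will be considered as having no reported bleeding, no cramping, no other contraceptive use"; a single missing item is treated the same way. SAP 9.2 repeats this for the primary Pearl Index: diary days with no information on other methods "will be considered days when no other birth control method use took place". It also excludes from the denominator every 28-day cycle in which another method was reported.

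**The concern.** Each rule is reasonable alone. Preferring a daily record to later recall is sound, and so is a stated convention for blanks. Together they let an empty record outrank a filled one. The SAP trusts the recalled copy when no original arrives, but drops it when an original arrives with nothing written for that day, so returning a blank page removes information the sponsor already holds.

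The effect has a direction. A blank can remove a report of use, bleeding or cramping but cannot create one. For other contraception, which the diary records throughout treatment, a lost report can leave a cycle in the Pearl Index denominator. Pregnancies in the numerator do not depend on the diary, so the index can only move down.

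In Months 1-24 the diary is also the source for bleeding and cramping days and for the menstrual TEAEs defined in SAP 11.4.1 and 11.5.1, which require a ticked diary box. Those counts can also only move down.

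**Working it through.** The plan gives no figure to reproduce on this point. The check is a trace of the rules, followed by arithmetic for scale.

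**1. Trace.** For one study day, the original and the copy can each be absent, blank, *no* or *yes*, which gives 16 combinations. The table shows the value analysed under SAP 5.3.1 with 5.3.2 and 9.2. An arrow shows a change if the copy is used when the original is blank.

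| Original | Copy absent | Copy blank | Copy *no* | Copy *yes* |
|---|---|---|---|---|
| absent | none | none | no | yes |
| blank | none | none | none → no | none → **yes** |
| *no* | no | no | no | no |
| *yes* | yes | yes | yes | yes |

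Since *none* and *no* are the same analysis value, one cell changes in substance: original blank, copy *yes*.

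**2. From day to cycle.** One reported day of other-method use excludes a cycle. The cycle is therefore wrongly kept only if every such day reported in it falls on a blank original day. Likewise, a woman loses a diary-defined TEAE only if all her qualifying ticks are lost.

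**3. Effect on the Pearl Index.** SAP 9.2 gives index = 1300 × pregnancies / cycles. If wrongly kept cycles equal a fraction p of the correctly counted cycles, the reported index is the correct one divided by (1 + p), a relative shortfall of p/(1 + p). This does not depend on the total number of cycles. The documents give no value for p, so the range is assumed. The starting index of 0.280 is the ceiling assumed in SAP 4.

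| p (assumed) | Relative shortfall | Reported index if correct index is 0.280 | Difference |
|---|---|---|---|
| 0.5% | 0.5% | 0.280/1.005 = 0.2786 | 0.0014 |
| 1% | 1.0% | 0.280/1.01 = 0.2772 | 0.0028 |
| 3% | 2.9% | 0.280/1.03 = 0.2718 | 0.0082 |

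**4. Effect on the precision criterion.** SAP 10.1 looks for an upper 95% limit no more than 1 unit above the estimate. Take 10,000 counted cycles (the two-year minimum in SAP 4), 2 pregnancies (assumed) and an exact Poisson upper limit (assumed): 1300 × [χ²(0.975; 6 df)/2] / cycles. Then remove the cycles that should not have been counted.

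| Share of the 10,000 wrongly kept (assumed) | Correct cycles | Index | Upper limit | Gap |
|---|---|---|---|---|
| 0% | 10,000 | 0.260 | 0.939 | 0.68 |
| 1% | 9,900 | 0.263 | 0.949 | 0.69 |
| 5% | 9,500 | 0.274 | 0.989 | 0.72 |
| 10% | 9,000 | 0.289 | 1.044 | 0.75 |

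The gap stays below 1 unit even at 10%. This is one illustrative case; it was not repeated for later years with less exposure.

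**The case against.** The strongest reply is that the situation should be rare. The copy exists because the original was not brought, not because it was not kept. The diary is meant to be completed daily, so the days being recalled should already be filled in at home. Protocol 6.4 has sites review returned diaries for completion and confirm that other contraception is entered correctly, and Protocol 8 provides for queries on incomplete data. Visits are up to six months apart after Month 6, so day-level recall may be poor and preferring the original is defensible. SAP 5.3.1 also promises to present the extent of missing diary records. Serious bleeding or cramping, and events leading to removal or unrelated to the IUS or a menstrual condition, reach the adverse event CRF by another route.

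Most of this stands as an argument about size, and it rules out calling the problem likely. It does not supply the missing rule. Nothing directs the analyst to the copy when the original day is blank. The general statement in SAP 5.3 that all available data will be used does not displace the specific rule for duplicates. The planned summary of missing diary records is not described as matching blank originals to filled copies. The Pearl Index without cycle exclusions (SAP 9.3) ignores other-method use altogether, so it cannot reveal the loss.

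Stronger readings are tempting but not supported. A reader might infer that the SAP expressly orders blanks to prevail; it does not, and the result follows from an unqualified rule combined with the blank-as-none convention. A reader might infer that the copy is erased; it is retained, and only the analysis value is affected. A reader might also infer that any single lost day returns a cycle to the denominator or removes a TEAE; step 2 shows that all the relevant days must be lost.

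**Conclusion.** The gap is real but narrow. On the text as written, a positive copy entry facing a blank original day is analysed as none. The consequence is one-directional: a slightly low Pearl Index where a cycle's only reported other-method days are lost, and under-counted bleeding and cramping days in Months 1-24, with a diary-defined TEAE missed if all its qualifying ticks are lost.

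The frequency is undocumented, and the effect on the index is probably very small: about 0.008 on 0.280 at the top of the assumed 0.5% to 3% range. It is not expected to change the precision conclusion, and the documents do not support saying that it would. The loss of bleeding and cramping days cannot be sized from the documents. The case for changing the rule rests on its direction, on its inconsistency with the SAP's own acceptance of the copy when no original arrives, and on how easily it can be avoided.

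**What to change.** Add to SAP 5.3.1, before the next database cut-off, that the original takes precedence wherever it has an entry, but that where the original's whole day is blank and the clinic copy has an entry, the copy's entry is used.

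Limit any item-by-item fallback to items where a blank can be told apart from *none* or *no*. Do not apply it to the two tick boxes (cramping worse, bleeding heavier, than when not using hormones) on days the original is otherwise completed. There an unticked box is itself the negative answer, and fallback would let recall override a completed daily record.

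Report the number of days and cycles the rule changes. If the sponsor prefers to keep the present rule, a sensitivity analysis counting other-method use reported on either version would show the size of the effect.

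The cost is one sentence and one merge step on data already held, with no new collection. The downside is that a few days will rest on recall, possibly over as long as six months between visits; the SAP already accepts this when the original is never returned.

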9.8 Key Secondary Outcomes

The Pearl Index analysis described above for the primary outcome will also be performed for use during years 3, 4, 5, 6, 7, 8, 9 and 10 using the MITT population. The Pearl Index will be calculated for use during years 3, 4, 5, 6, 7, 8, 9 and 10 with a goal of each having acceptable precision (defined as the upper bound of the 95% confidence interval being no more than 1 unit above the point estimate). Other Secondary Outcomes

All secondary outcomes will be analyzed using the Safety Population unless noted otherwise.

- **Pregnancy Rates**

Pearl indices and life table pregnancy analyses will also be prepared for the PP population during years 3, 4, 5, 6, 7, 8, 9 and 10 unless the populations are essentially the same as the MITT population. Kaplan-Meier methods will be used to estimate the cumulative pregnancy percentage for years 1 through 10 for each treatment group using the MITT population.

- **IUS Continuation Rates**

Cumulative IUS continuation rates at 1 year, 2 years, 3 years, 4 years, 5 years, 6 years, 7 years, 8 years, 9 years and 10 years will be summarized for each treatment group, as applicable, using Kaplan-Meier methods.

- **IUS Expulsion Rates**

Cumulative IUS expulsion rates at 1 year, 2 years, 3 years, 4 years, 5 years, 6 years, 7 years, 8 years, 9 years and 10 years will be summarized for each treatment group, as applicable, using Kaplan-Meier methods.

- **IUS Safety-Related Removal Rates**

Cumulative IUS safety-related removal rates at 1 year, 2 years, 3 years, 4 years, 5 years, 6 years, 7 years, 8 years, 9 years and 10 years summarized for each treatment group, as applicable, using Kaplan Meier methods.

- **Vaginal Bleeding Patterns**

Vaginal bleeding patterns (none, spotting, and light, normal, or heavy flow [bleeding]) will be summarized by incidence and duration of bleeding. Baseline vaginal bleeding is recorded on the Menstrual History CRF based on menstrual characteristics when not using hormonal contraception.

Based on WHO terminology, bleeding and spotting are defined as:

- Bleeding: any bloody vaginal discharge for which protection, such as pads is used.
- Spotting: any bloody vaginal discharge for which protection is not used (for women who use mini pads for daily protection, extra protection is not required); if spotting and bleeding occur on the same day, it is recorded as a bleeding day.

- **Dysmenorrhea**

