11.5 Menstrual Related Bleeding

11.5.1 Up to Month 24

For the first 24 months of the study a subject will be defined as having a menstrual Bleeding TEAE if:

- The subject diary question, “Check box if bleeding today is heavier than when not using hormones” is marked

AND

- Baseline bleeding that is the same or worsens from what is indicated on the Menstrual History CRF based on menstrual characteristics when not using hormonal contraception.

If a bleeding TEAE is recorded on the Adverse Event CRF and not on the subject diary due to the event being an SAE, results in IUS removal or is not related to the IUS or menstrual condition, the subject will be counted as having a bleeding TEAE. Subject incidence of bleeding TEAEs will be described within the overall adverse event incidence summary.

11.5.2 After Month 24

For Months 25 through 121, bleeding TEAEs will be recorded only in the Adverse Event CRF and not determined based on daily subject diary responses. During these months there will be no subject diary for menstrual changes and instead a periodic (every 3 months) form characterizing their bleeding will be used. Self-reported bleeding TEAEs will be recorded on the Adverse Event CRF.

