11.6 Diary Reported Bleeding and Cramping/Pain Analysis

11.6.1 Months 1-24

For each 28-day cycle and each 84 and 90 day interval post-insertion, the incidence of on-treatment cramping/pain (none, mild, moderate, severe) and bleeding (none, spotting, light flow, medium flow, heavy flow) will be calculated based on diary entries and presented by treatment group. Summaries of the following types will be presented:

- Incidence of cramping/pain by 28-day cycle and 84 and 90 day intervals post-insertion (none vs. ≥ 1 day; 1-3, 4-7, >7 , and >20 days)

- Incidence by of bleeding by 28-day cycle and 84 and 90 day intervals post-insertion (none vs. spotting vs. bleeding; none vs. ≥ 1 day; 1-3, 4-7, >7 , and >20 days; no bleeding vs. any bleeding)
- Incidence of cramping/pain by highest severity or bleeding by greatest intensity by cycle and 84 and 90 day intervals post-insertion. At each level of subject summarization a subject is classified according to the highest severity or intensity if the subject reported one or more events.

Descriptive continuous-based statistics (mean, standard deviation, median, minimum, maximum) will be used to summarize the number of days of reported cramping and bleeding and/or spotting during each 28-day cycle and each 84 and 90-day interval. The number of spotting days and the number of bleeding days (light flow, moderate flow, heavy flow combined and each category separately) will also be summarized using this approach. For cramping/pain, this will also be presented within each severity rating, i.e., the total number of reported days will be broken down into the number of days of mild, moderate, and severe cramping/pain.

11.6.2 After Month 24

The incidence of reported cramping every three months after Month 24 will be reported using the categories which appear in parentheses below:

- Over the last 3 months has the subject had any menstrual cramping/pain? (Yes/No)
- Did the cramping/pain occur mainly when the subject was having any bleeding or spotting? (Yes/No)
- The worst cramping/pain experienced during these months (mild, moderate, severe)

The incidence of bleeding and/or spotting will be presented in a similar fashion based on the following questions and categories of response:

- Over the last 3 months has the subject had any menstrual bleeding/spotting?
- What was the main pattern of bleeding/spotting the subject experienced for these months? (Just Spotting, Irregular Bleeding, Regular Bleeding [periods])

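### For women who completed only the early diary, coding Bleeding as Normal Flow makes light and heavy flow zero by construction in Months 1-24, and may distort diary bleeding TEAEs

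*SAP*

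**What the plan says.** SAP 5.3.1 sets out the analysis scale in rising order: "Bleeding: None, Spotting, Light Flow, Normal Flow, Heavy Flow". A note beneath it adds: "In an early version of the diary, this information was recorded as None, Spotting, or Bleeding". The note then gives the rule: "In the analysis, if the subject did not complete a revised diary, the category of" bleeding is taken to be Normal Flow.

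Two sets of outputs use the resulting grade.

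- **Flow tables.** SAP 11.6.1 summarizes diary bleeding for Months 1-24 by flow category, per 28-day cycle and per 84- and 90-day interval. It counts bleeding days both combined and grade by grade, and adds: "Incidence of cramping/pain by highest severity or bleeding by greatest intensity by cycle and 84 and 90 day intervals post-insertion". Its middle grade is called medium in one place and moderate in another; I take both to be the Normal Flow of 5.3.1.
- **Bleeding TEAEs.** SAP 11.5.1 defines a diary bleeding TEAE up to Month 24 by two criteria joined by AND. The first is that the diary item "Check box if bleeding today is heavier than when not using hormones" is marked. The second reads: "Baseline bleeding that is the same or worsens from what is indicated on the Menstrual History CRF". On the source of baseline, Protocol 9.8 says: "Baseline vaginal bleeding is recorded on the Menstrual History CRF based on menstrual characteristics when not using hormonal contraception". Neither document shows that form's response categories.

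**The concern.** The rule fills in a grade that was not collected. SAP 5.3.2 says missing diary bleeding data will not be imputed, but here one fixed grade is assigned and then tabulated as if it had been observed. Bleeding pattern is a stated secondary objective, so readers will take the light, normal and heavy columns at face value.

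The same grade may decide whether a bleeding TEAE is counted. Under Protocol 7.12.1 the diary serves as the adverse event record for menstrual bleeding through Month 24. The general AE form takes such bleeding only if it is serious, leads to IUS removal, or is unrelated to the IUS or a menstrual condition. Any other event that fails the diary test has no second route into the count, and diary bleeding TEAEs feed the overall adverse event incidence summary.

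The plan describes no flag, count or sensitivity display for women on the early diary.

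**Working it through.** The plan gives no figure to reproduce, so the check applies the stated rules directly.

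**1. Flow grades.** The early diary allows None, Spotting or Bleeding. After the recode the possible grades are None, Spotting and Normal. Light and Heavy cannot occur on these records.

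Let e be the share of bleeding days that are recoded, and L, N and H the true shares of light, normal and heavy days, assumed the same on both diary versions. The tables then show:

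- light = (1 - e) × L
- normal = (1 - e) × N + e
- heavy = (1 - e) × H

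Neither e nor the true split is in the documents. Purely as an illustration, take L, N, H = 45%, 40%, 15%:

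| e | light | normal | heavy |
|---|---|---|---|
| 0 | 45% | 40% | 15% |
| 0.2 | 0.8 × 45 = 36% | 0.8 × 40 + 20 = 52% | 0.8 × 15 = 12% |
| 0.6 | 0.4 × 45 = 18% | 0.4 × 40 + 60 = 76% | 0.4 × 15 = 6% |
| 1 | 0% | 100% | 0% |

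**2. Women who switched.** The recode is stated only for this case: "if the subject did not complete a revised diary". The SAP does not say whether that means at any time or for the same days. For a woman with early pages followed by revised pages, the coding of her early Bleeding days is not defined.

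**3. Bleeding TEAE.** Three assumptions are needed, none shown in the documents: the Menstrual History CRF uses the same scale with a Heavy grade; criterion 2 compares the day's diary grade with that baseline; and the early diary carried the 'heavier' box. Assume the box is marked, and that criterion 2 is met when diary grade ≥ baseline grade. Each cell shows the result on the revised diary, then after the early-diary recode:

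| Baseline | Spotting | True Light | True Normal | True Heavy |
|---|---|---|---|---|
| Light | no / no | yes / yes | yes / yes | yes / yes |
| Normal | no / no | **no / yes** | yes / yes | yes / yes |
| Heavy | no / no | no / no | no / no | **yes / no** |

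Two of the 12 cells change, in opposite directions. A woman with Heavy baseline meets criterion 2 at 0 of 4 true-flow levels after the recode, against 1 of 4 on the revised diary. A woman with Normal baseline and truly light flow meets it only because of the recode.

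**The case against.** The best defence is that the rule is narrow. It covers only women without a completed revised diary, and the none/spotting/bleeding and any-bleeding summaries are untouched. SAP 11.6.2 grades heaviest flow again after Month 24. No formal testing is planned, and the Pearl Index does not use flow grade. All of this stands and limits the reach of the point, but it does not repair the Months 1-24 intensity tables.

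A reader might infer more than the documents support:

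- **That every early-diary Bleeding day becomes Normal Flow, and that these women can never show light or heavy flow.** The rule is conditional, women who switched can have graded days, and the later form records Light and Heavy.
- **That bleeding TEAEs are undercounted.** This rests on the three assumptions above, and criterion 2 is loosely worded. The error also runs both ways. The gained cell needs a woman with lighter flow than baseline to mark the 'heavier' box, which seems less likely than the lost cell, but the documents give no frequencies to settle the net direction.
- **That the recode creates false differences between LNG20 and Mirena, or between inserters.** An early diary, the end of Mirena recruitment and the inserter change all belong to the study's earlier period, so uneven exposure is plausible. But the diary revision is not dated and no shares are given; with equal e in two groups there is no between-group artefact. SAP 3 also leaves diary flow tables out of its list of Mirena comparator outputs, although 11.6.1 presents them by treatment group. Diary bleeding by inserter would arise only if judged relevant under SAP 5.9.

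**Conclusion.** The point holds in a limited form. For women who completed only the early diary, the Months 1-24 light and heavy counts in SAP 11.6.1 are zero because of the coding rule, whatever their bleeding was. This follows from the text alone. The rule for women who switched diaries is missing.

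The TEAE effect is conditional on the form contents and on one reading of criterion 2. Under those assumptions, a heavy-baseline woman cannot have a diary-derived bleeding TEAE on recoded days, and a normal-baseline woman with light flow could wrongly meet criterion 2. The number of women affected and the net direction are unknown, and a between-group artefact is possible but not shown. The consequences lie in secondary and safety summaries, not in the primary efficacy result.

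**What to change.** 1. Code every early-diary Bleeding day, at the day level and whether or not the woman later switched, as bleeding with intensity not recorded.
2. Keep these days in the none/spotting/bleeding and any-bleeding counts. Exclude them from the light/normal/heavy and greatest-intensity summaries and denominators, and state how intervals that straddle a switch are handled.
3. Keep one bleeding TEAE definition for the main table. State what criterion 2 compares and how it is settled when no grade exists. On the reading used above, any Bleeding day meets a Light baseline, while Normal and Heavy baselines are undetermined.
4. Add a sensitivity count that treats criterion 2 as met on early-diary days where the 'heavier' box was available and marked. This should not replace the main definition: using the box alone for early-diary women would give them a looser test than other women and could itself create group differences in adverse event incidence.
5. Report the number of early-diary women by treatment group and inserter.

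The cost is SAP wording, a flag in the diary dataset and one extra count. No new data are needed. The intensity tables will rest on fewer diary days and women, which matters most if early diaries are common in the small Mirena group.
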